#### 8.2.3 Multivariate analysis

We will apply 2 modelling strategies:

#### Case- Crossover design

The association between DDS events and episodes of cardiac arrhythmia will be assessed in a casecrossover design . This method has been used previously to study triggers of acute cardiovascular events . We will define case periods by the time of each confirmed episode of cardiac arrhythmia, rounded to the nearest hour. We will match control periods on weekday and hour of the day within the same calendar month. Conditional logistic regression analysis will be performed to analyze the exposure odds ratio with 95% confidence intervals on risk of cardiac arrhythmia.

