# 2 STUDY OBJECTIVES

# 2.1 Primary Objective

The primary objective of this panel study will be to quantify the vulnerability of adults with atrial fibrillation (AF) during DDS outbreaks and provide evidence-based estimates demonstrating which intervention/ recommendations work best in mitigating adverse health effects in this group of patients (primary outcome: reduction of atrial fibrillation burden by 20%) after randomization to three parallel intervention groups:

- a) no intervention for DDS
- b) intervention for outdoor exposure reduction, and
- c) interventions for both outdoor and indoor exposure reduction

The primary health outcome will be defined by using every detected high atrial frequency episode of >330 ms (180 beats per minute) lasting for longer than 30 s with an atrial sensitivity of 0.5 mV (assumed as an episode of AF). AF burden is defined as the overall time percentage with AF during the observed period. For the primary analysis, we will compare the combined effect in the two intervention groups versus the control group. Secondarily, the effectiveness of each intervention will be compared versus the control group and to each other.

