# 4 STUDY DESIGN

Type of study: Randomized clinical trial (Behavioural Intervention)

Patients with AF will be recruited during DDS outbreaks and will be randomized into three parallel groups to receive:

- a) No intervention for DDS,
- b) Intervention for outdoor exposure reduction, and
- c) Interventions for both outdoor and indoor exposure reduction.

Disease-related adverse health outcomes will be assessed in all the parallel arms of the study.

Previous publications of the MEDEA partners (Achilleos et al, 2014; Gerasopoulos et al, 2006; Krasnov et al, 2014), indicated that 2/3 of each year's DDS events in the Eastern Mediterranean region appear during February-May, with 10-15% of the days during this period being "DDS days". Thus we will perform this public health intervention study during February–May of 2019 and 2020.

Study population and location: Men and women with prior implantation of a dual lead (atrial and ventricular) pacemaker or ICD, will be recruited from the cardiac arrhythmia clinic at the Nicosia General Hospital of Cyprus (n=156) in project years 2018-2019 and 2019-2020. Each patient will have assessment of health outcomes during only one high DDS period.

Duration of the study: A feasibility trial and refinement of protocols and tools will be performed in the high DDS period of 2018. In the fall of 2018 and 2019, MEDEA personnel will start recruitment efforts to detect eligible AF patients for participation in the study during the high DDS periods of February-May 2019 and 2020.

Assessment of health outcomes:

- The occurrence of AF/ventricular arrhythmia episodes will be recorded daily using the already implanted participants' pacemakers or ICD during the 4-month study period. The recorded episodes will be downloaded with interrogation of the pacemaker or ICD during a visit to the Arrhythmia Clinic after the end of the study period.
- Phone interviews every 1 month throughout the high DDS outbreaks season will be carried out. Data collected will include symptoms of fatigue, change in medication use and unscheduled visits to health professionals for heart arrhythmias/episodes.
- Continuous recordings of biological parameters (pulse rate, pulse rate variability and temperature) obtained by wearing smart watch sensors and uploaded on line to the secure e-platform.

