# 6 STUDY INTERVENTIONS

# 6.1 Interventions, Administration, and Duration

Following recruitment, we will randomize participants with a 1:1:1 ratio to three parallel groups to receive:

a) no intervention for DDS

b) intervention for outdoor exposure reduction, by reducing the time spend outdoors and by avoiding physical activity

c) interventions for outdoor (as above) and indoor exposure reduction (by minimizing home ventilation and filtering indoor air).

In the indoor intervention arm of the study, exposure reduction measures will be applied in the patient's household/bedroom settings.

After randomization, and prior to the high DDS season, each eligible participant will complete a questionnaire, providing socio-demographic characteristics, detailed medical and medication history, and will be trained in the tools and procedures to be followed during the monitoring sessions while in the community. The study design offers also the opportunity to assess:

- outdoor exposures to PM,
- indoor exposures to PM and
- related health outcomes in three parallel groups during the same DDS events with and without intervention measures (Figure C8.1).

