## Figure C8.1. Study Year 1 (February-May 2019) - 78 patients with AFIB in each study site (Beer Sheba-Israel, Nicosia-Cyprus & Heraklion-Crete) to be randomized to three levels of intervention

### Life+ MEDEA Action C7 Protocol, Version 1.0

## 6.2 Handling of Study Interventions

A bidirectional, patient-centered e-Platform will be created to:

- Communicate promptly forecast alerts to individuals about upcoming DDS events through smartphone applications and text messaging
- Disseminate exposure reduction guidelines

In particular, in the group where there will be intervention for outdoor exposure reduction, the intervention will be carried out by:

- Informing the participant for upcoming desert dust storm episodes.
- Simultaneous transmission of instructions to patient's smartphone to reduce outdoor exposure during the episode (stay indoors, avoid intense physical activity outdoors, avoid competitive sports, avoid unnecessary walks).

In the group where there will be interventions for outdoor and indoor exposure reduction, the intervention will be carried out by:

- Informing the participant for upcoming desert dust storm episodes.
- Simultaneous transmission of instructions to patient's smartphone to reduce a) outdoor exposure during the episode (stay indoors, avoid intense physical activity outdoors, avoid competitive sports, avoid unnecessary walks), and b) indoor, home exposure (closed windows and doors, sealing possible cracks around windows and doors in order to minimize home ventilation, and using an air cleaner in order to filter indoor air).

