#### Randomization

Following the eligibility assessment, participants will be randomized using PASS 14 software that allows for random number generation. Randomization will be carried out with a 1:1:1 ratio to three parallel groups:

- a) Control group A: No intervention for DDS,
- b) Intervention group B: Intervention for outdoor exposure reduction, and
- c) Intervention group C: Intervention for outdoor and indoor exposure reduction (patient's household/bedroom settings)
- 7.2.3 Follow-up Assessments
  - Intervention mid-point assessment April 2019/2020:
    - Current medications
    - Intervention discontinuation
    - Telephone questionnaire
    - Daily recordings of AF/ventricular arrhythmia episodes
    - Continuous recordings of biological parameters (pulse rate, pulse rate variability, temperature)
    - Adverse events

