### Hierarchical model

Generalized Linear Model will be used to fit a Poisson regression of daily AF episodes against temporal variables and DDS data based in hierarchical model. Data model with random effect include repeated episodes of AF in each patien, the intervention groups and the 3 sites of the research. Date model with fixed effect include DDS event during the period of the study.

Analysis will be performed using R Project for Statistical Computing version 3.0 or higher and IBM SPSS software version 23 or higher.

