Summaries of main variables will be presented in form of means and standard deviations for normal distributed quantitative variables, medians and ranges for non-normal distributed quantitative variables, distribution in percentages for qualitative variables.

Univariate analysis

Univariate analysis will be mostly used for analysis initial datasets consisted of personal data records.

The method of analyses for continuous variables will be parametric using Paired and Unpaired t-test and Repeated Measurements ANOVA.

Non-parametric procedures will be used if parametric assumptions could not be satisfied, even after data transformation attempts. These tests will include Mann-Whitney, Wilcoxon and Spearman Correlation tests.

Categorical variables will be tested using Chi-Square test.

Multivariate analysis

We will apply 2 modelling strategies:

Case- Crossover design

The association between DDS events and episodes of cardiac arrhythmia will be assessed in a casecrossover design ⁽¹⁰⁾. This method has been used previously to study triggers of acute cardiovascular events ⁽¹¹⁾. We will define case periods by the time of each confirmed episode of cardiac arrhythmia, rounded to the nearest hour. We will match control periods on weekday and hour of the day within the same calendar month. Conditional logistic regression analysis will be performed to analyze the exposure odds ratio with 95% confidence intervals on risk of cardiac arrhythmia.

Hierarchical model

Generalized Linear Model will be used to fit a Poisson regression of daily AF episodes against temporal variables and DDS data based in hierarchical model. Data model with random effect include repeated episodes of AF in each patient, the intervention groups and the 3 sites of the research. Date model with fixed effect include DDS event during the period of the study.

Analysis will be performed using R Project for Statistical Computing version 3.0 or higher and IBM SPSS software version 23 or higher.

3. References

Voorend-van Bergen S, et al. Monitoring childhood asthma: web-based diaries and the asthma control test. J Allergy Clin Immunol. 2014;133:1599-605.

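### Neither dust-storm model separates the arms, so if the interventions work its DDS coefficient understates vulnerability without intervention

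*Protocol*

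**What the plan says.** Protocol 2.1 gives the primary objective two parts. The first is to "quantify the vulnerability of adults with atrial fibrillation (AF) during DDS outbreaks"; the second is to find which intervention mitigates the effects best. No estimand is given for the first part: the text does not say whether vulnerability means the response without intervention or the average over all arms.

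Protocol 6.1 states that "we will randomize participants with a 1:1:1 ratio to three parallel groups". Only one group is left alone: "Control group A: No intervention for DDS" (7.2.2). In the other two, the advice is tied to the dust event: "Simultaneous transmission of instructions to patient's smartphone to reduce outdoor exposure during the episode" (6.2). The third group also receives indoor measures.

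Protocol 8.2.3, repeated in SAP section 2, lists two modelling strategies:

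- **Case-crossover.** "The association between DDS events and episodes of cardiac arrhythmia will be assessed in a casecrossover design", and "Conditional logistic regression analysis will be performed to analyze the exposure odds ratio with 95% confidence intervals on risk of cardiac arrhythmia". No arm term, stratum or restriction is mentioned.
- **Poisson.** Patient, intervention group and site are listed as random effects. For the fixed part, the text reads "Date model with fixed effect include DDS event during the period of the study". No DDS-by-arm term is listed.

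SAP section 2 also gives a mixed model (Equation 1), written for the asthma panel, with exposure slopes specific to each group. It says these formulas will be used for the AF outcomes to quantify the benefit of exposure reduction. The AF exposure data come from a random subgroup of 20 households per site.

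**The concern.** With 1:1:1 allocation, two of every three patients are asked to avoid dust in the very periods that both models treat as exposed. If the advice works, arms B and C respond less to a DDS day than arm A. A single DDS coefficient then averages one unmitigated response and two mitigated ones.

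The self-matching in the case-crossover does not remove this, because the advice comes and goes with the exposure. A random intercept for arm does not remove it either. A random DDS slope by arm would still leave the fixed DDS term as an average over arms.

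A small coefficient could therefore mean that patients are not very vulnerable, or that they are vulnerable and the intervention protected them. Protocol 3.2 intends the vulnerability findings to inform policy, so the two need to be told apart.

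**Working it through.** **Figures in the plan.** The documents state no size for the DDS effect on AF, so there is no figure to reproduce for this association. The AF power statement (Protocol 8.1) concerns the arm comparison only. Its effect size is consistent: 20% of a 15% burden is 3 percentage points, and 0.03 × 1440 = 43.2 minutes per day, against 43 stated.

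**Inputs.**
- Allocation 1:1:1 (Protocol 6.1).
- DDS on "10-15% of the days during this period" (Protocol 4).
- Control burden 15%, reduction 3 points (Protocol 8.1).
- Assumed: RR_A, the rate ratio for DDS against other days in arm A.
- Assumed: r, the fraction of the dust excess removed in B and C, taken as equal in both.

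**Formula.** The intervention-arm ratio is RR_I = 1 + (RR_A − 1)(1 − r). With equal arms and equal background rates, the common coefficient targets about (RR_A + 2·RR_I)/3. Hence

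pooled excess = (RR_A − 1) × [1 + 2(1 − r)]/3 = (RR_A − 1) × (1 − 2r/3).

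If the two arms differ, the factor is 1 − (r_B + r_C)/3.

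| r | Share of excess kept | Pooled, RR_A = 1.3 | Pooled, RR_A = 1.5 | Pooled, RR_A = 2.0 |
|---|---|---|---|---|
| 0 | 100% | 1.30 | 1.50 | 2.00 |
| 0.2 | 87% | 1.26 | 1.43 | 1.87 |
| 0.5 | 67% | 1.20 | 1.33 | 1.67 |
| 0.8 | 47% | 1.14 | 1.23 | 1.47 |
| 1 | 33% | 1.10 | 1.17 | 1.33 |

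**Using the plan's own effect size.** Suppose the whole 3-point reduction falls on DDS days, all dust excess is removed (r = 1), and episode rates follow burden. Burden on other days is then 15 − 3 = 12%. On DDS days in arm A it is 12 + 3/p, where p is the share of DDS days.

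| p | DDS-day burden, arm A | RR_A | Pooled RR | Pooled log effect / arm A log effect |
|---|---|---|---|---|
| 10% | 42% | 3.50 | 1.83 | 48% |
| 12.5% | 36% | 3.00 | 1.67 | 47% |
| 15% | 32% | 2.67 | 1.56 | 45% |

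This is an extreme case, but it is the one in which the assumed benefit comes entirely from removing the dust effect.

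**Simulation check.** The setting was 324 patients, 120 days, 12.5% DDS days, an assumed 0.5 episodes per day with a log-normal patient effect, and 100 runs per setting. Each data set was analysed by a time-stratified case-crossover and by a Poisson model with a patient intercept and one DDS effect. The two models agreed to within 0.01.

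| True RR_A | Pooled, r = 0 | Pooled, r = 0.5 | Pooled, r = 1 | Arm A only (all r) |
|---|---|---|---|---|
| 1.3 | 1.30 | 1.20 | 1.10 | 1.29–1.30 |
| 3.0 | 3.01 | 2.32 | 1.66 | 2.98–3.02 |

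**Precision.** For the case-crossover at RR_A = 1.3, the standard error of the log effect was 0.023 pooled and 0.040 in arm A. The ratio is 0.040/0.023 = 1.74, close to √3 = 1.73. For the ratio of two arms' DDS effects it is about √2 × 0.040 = 0.057. The absolute values depend on the assumed episode rate and on independent episodes; the ratios between them matter here.

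**The case against.** Four objections have force.

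1. **Equation 1.** A reader might infer that the two models are the only planned link between dust and AF. The SAP does not support that, because Equation 1 has group-specific exposure slopes and is extended to the AF outcomes. A slope on measured exposure could in principle describe vulnerability per unit of exposure. But its stated purpose for AF is the benefit of exposure reduction, and its exposure data come from about 3 × 20 = 60 households, against 324 patients to be analysed. It does not supply the DDS vulnerability estimate.

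2. **Silence is not pooling.** The case-crossover text does not say that the arms are combined; this is inferred because no arm term is mentioned. The Poisson text does not ignore arm, and does not say whether the random effect is an intercept or a slope. Both points stand. Yet the models fitted as written give a DDS effect averaged over arms.

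3. **The bias is conditional.** A reader might infer that vulnerability will be underestimated in any case. That holds only if the advice is followed and works, and if the target is the response without intervention. At r = 0 there is no bias. If advice raised the dust excess by 20%, the pooled RR would be too high (1.34 against 1.30). The trial is, however, powered on the assumption that the interventions work.

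4. **Carry-over.** One might add that sealing done in arm C persists into the matched control days. Protocol 6.2 ties the instructions to the episode, so this is speculative. If it lowered risk on control days, it would raise arm C's ratio and offset the understatement. It forms no part of the case.

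**Conclusion.** The point holds as a conditional one. Neither model in Protocol 8.2.3 and SAP section 2 lets the fixed DDS effect differ by arm or confines it to the control arm. If the interventions work, the resulting coefficient keeps about 1 − 2r/3 of the excess seen without intervention, so a third is lost at r = 0.5 and two thirds at r = 1. The assumptions are equal arms, equal background rates and the same r in B and C. RR_A and r are not in the documents.

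A reader might also infer that the trial's main result is compromised. It is not. Protocol 2.1 sets the primary analysis as both intervention groups combined against control on AF burden, and that randomised comparison does not use the DDS coefficient. The two models concern episodes, not burden. This is a cheap improvement that should be made before analysis, because it decides whether the first part of the primary objective gets an interpretable answer.

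**What to change.** In Protocol 8.2.3 and SAP section 2:

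- Add a fixed DDS-by-arm interaction to the case-crossover and Poisson models.
- Report the arm A odds or rate ratio for DDS as the estimate of vulnerability.
- Report the B/A and C/A ratios of DDS effects as secondary estimates of mitigation on DDS days. Describe them as between-patient comparisons of within-patient contrasts.
- Do not report the all-arm DDS coefficient as vulnerability.
- State how Equation 1 relates to these estimates and what it is meant to estimate for AF.

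The cost is wording and an interaction term; no new data are needed. The vulnerability estimate rests on one third of the patients, so its standard error is about 1.7 times larger. The B/A and C/A ratios are less precise still, with a standard error about 1.4 times that of the arm A estimate. Modest mitigation would not be detectable. At RR_A = 1.3 and r = 0.2, RR_I = 1 + 0.3 × 0.8 = 1.24, and the log difference is ln(1.30/1.24) = 0.047 against a standard error of about 0.057, which gives z of about 0.8 even at the assumed episode rate. The ratios should therefore be presented as estimates with intervals, not as tests on which a conclusion depends.

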# 3.2 Study Rationale

#### Desert dust storm events across Southern Europe

A dust storm is a phenomenon common to arid and semi-arid regions. In the EU, the term "Desert Dust Storms (DDS)" is used in the context of sandstorms originating primarily from the Sahara desert but also from the Arabian–Negev desert. The term DDS refers to the condition created when finer sand particulate matter (PM) from the desert surface is transported over a long distance. DDS pose a major risk to populations residing in affected areas, such as in Mediterranean countries belonging to the global dust belt, extending from West Africa to the Arabian Peninsula (Querol et al., 2009). During DDS events, which can last for several days,  $PM_{10}$  levels are considerably higher than the 2005 EU daily limit value of 50 µg/m^3 (Achilleos et al, 2014). Dust PM is mostly composed of rock-forming and clay minerals and they may carry microbial agents, such as bacteria, fungi and viruses (Griffin et al, 2007), and mix with anthropogenic atmospheric pollutants during transport.

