#### 8.1 Sample size consideration

There are no studies that evaluated the reduction in AF burden attributed to reduction in exposure to ambient air pollution.

We assume that the mean AF burden in the control group will be 15%+/-15%. We conservatively estimated the expected intervention effect to be 20% of relative reduction in AF burden. This is translated into the reduction of AF burden by mean of 43 minutes per 24 hours.

Group sample sizes of 108 and 216 achieve 81% power to show a difference in means when there is a difference of -3.0 between the null hypothesis mean difference of 0.0 and the actual mean difference of 3.0 at the 0.05 significance level (alpha) using a two-sided Mann-Whitney-Wilcoxon Test. These results are based on 2000 Monte Carlo samples from the null distributions: WeibullMS(15 15) and WeibullMS(15 15), and the alternative distributions: WeibullMS(15 15) and WeibullMS(15 15).

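### Case-crossover control hours may fall during ongoing AF, which pulls the dust odds ratio towards no effect if dust triggers AF; the interval can also be too narrow if episodes come in bursts

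*Protocol*

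**What the plan says.** Protocol section 8.2.3 (Case-Crossover design) and the section of the same name in the SAP use the same wording. Cases: "We will define case periods by the time of each confirmed episode of cardiac arrhythmia, rounded to the nearest hour". Controls: "We will match control periods on weekday and hour of the day within the same calendar month". Estimation: "Conditional logistic regression analysis will be performed to analyze the exposure odds ratio with 95% confidence intervals on risk of cardiac arrhythmia".

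Neither document says whether the time of an episode means its onset, requires a control hour to be free of AF, sets a minimum AF-free gap between two cases, or names a robust or clustered variance. Section 2.1 sets a low threshold for an AF episode, "lasting for longer than 30 s with an atrial sensitivity of 0.5 mV", so many short episodes can count. The separate Poisson model (Hierarchical model) has a random effect for repeated episodes.

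The first half of the primary objective is to "quantify the vulnerability of adults with atrial fibrillation (AF) during DDS outbreaks". The case-crossover is one of the two modelling strategies listed in section 8.2.3. The primary analysis in section 2.1 is a different one: both intervention groups combined against control on AF burden.

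**The concern.** A case-crossover compares exposure at the moment an event began with exposure at other moments when it could have begun. Hours in which the patient is already in AF do not meet the second condition for an AF event. If dust raises AF onset, patients also spend more of their dust hours in AF, so the invalid control hours carry more than their share of dust. Exposure among controls is inflated and the odds ratio falls towards 1.

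The second issue concerns precision. Several episodes on one day share the same weekday-matched control days. With exposure defined by day, they contribute nearly the same comparison several times, and conditional logistic regression treats each as new information.

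At stake is an understated estimate of how vulnerable AF patients are to dust, with an interval that may not show its true uncertainty.

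**Working it through.** **The plan's own figure.** There is none to reproduce: the case-crossover section gives no event count, power or odds ratio.

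**Inputs from the documents.** Burden, Protocol section 8.1: "We assume that the mean AF burden in the control group will be 15%+/-15" per cent, read as mean 15% and SD 15%, in line with the Weibull inputs. Dust prevalence, section 4: "with 10-15% of the days during this period" are dust days (12.5% used). Run length, section 3.2: "During DDS events, which can last for several days" (mean of 2.5 days assumed). Patients analysed: 324.

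**Assumed, because the documents do not give them.** True onset ratio 1.0, 1.25 or 1.5; mean episode 2-48 h; onset hazard multiplied by K = 1, 5 or 20 for 24 h after an episode ends (K above 1 represents bursts).

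**Step 1: share of control hours in AF.** Controls are drawn once per episode, so patients with many episodes dominate. If mean episode length is the same for all patients, a patient's episode count is proportional to burden b. The episode-weighted burden is then (mean² + SD²)/mean = (0.15² + 0.15²)/0.15 = 0.30, twice the patient mean. The simulations below gave 26-45%.

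**Step 2: attenuation in closed form.** In a two-state process with onset ratio R, burden under dust is b' = Rb/(Rb + 1 - b), and using all hours as controls gives R(1 - b')/(1 - b).
- b = 0.15, R = 1.5: b' = 0.225/1.075 = 0.209; ratio = 1.5 × 0.791/0.85 = 1.395.
- b = 0.30, R = 1.5: b' = 0.45/1.15 = 0.391; ratio = 1.5 × 0.609/0.70 = 1.304.

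This assumes that burden reaches its new level at once, so it can only be a guide.

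**Step 3: hour-level simulation.** 324 patients, 120 days, six site-year dust series, burden drawn from an exponential distribution with mean 15% (hence SD 15%), 100 runs per scenario. Results for a true ratio of 1.5:

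| Mean episode (h) | K | Control hours in AF | OR as planned | OR, AF hours dropped | Empirical SD / model SE, as planned |
|---|---|---|---|---|---|
| 2 | 1 | 0.261 | 1.299 | 1.424 | 0.81 |
| 12 | 1 | 0.293 | 1.338 | 1.490 | 0.80 |
| 48 | 1 | 0.304 | 1.387 | 1.505 | 0.91 |
| 2 | 5 | 0.315 | 1.299 | 1.458 | 1.30 |
| 6 | 5 | 0.376 | 1.329 | 1.558 | 1.12 |
| 2 | 20 | 0.348 | 1.268 | 1.428 | 1.20 |
| 6 | 20 | 0.444 | 1.275 | 1.522 | 1.24 |

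On the log scale the loss runs from 1 - ln 1.387/ln 1.5 = 19% to 1 - ln 1.268/ln 1.5 = 41%. For a true 1.25, the planned odds ratio averaged 1.15-1.20, and 1.22-1.28 with AF hours dropped. For a true 1.0 it averaged 0.99-1.00: no bias. A second simulation (episodes of 3-48 h) gave 1.30-1.35 for a true 1.5, and 1.44-1.47 with AF hours dropped.

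**Step 4: interval width.** A ratio above 1 in the last column means the planned interval is too narrow. Without bursts (K = 1) it was 0.75-0.91 over all three true ratios. With bursts it was 0.87-1.02 at no effect, 0.80-1.22 at 1.25 and 1.12-1.30 at 1.5. With 100 runs, an empirical SD has a relative error of about 1/√(2 × 99) = 7%.

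Those runs have episodes of hours. For many short episodes per day, a null simulation of daily counts was run (0.25-0.5 episodes per day, day-to-day correlation 0.5, negative-binomial dispersion k; all assumed). Over two sets of such runs, the nominal 5% test rejected 2-6% of the time without overdispersion and 12-38% with k of 1 to 0.5. Patient-clustered standard errors gave 2-11%. As an upper bound, m onsets in one burst with the same exposure contrast make the standard error too small by √m, for example twofold for m = 4.

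**The case against.** **The target may not be onset per hour at risk.** The section speaks only of an association between dust events and episodes. Episodes per calendar hour is a coherent quantity and matches the Poisson model of daily counts. This stands as far as the plan names no estimand. But the section presents the method as one for studying triggers of acute events, which points to onset, and a calendar-hour ratio mixes the effect of dust with the lost opportunity to start an episode.

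**The analysis is supporting, and the bias is towards no effect.** Both are true. A reader might infer that the trial's main conclusion is at risk or that attenuation creates false positives. Neither follows: the randomised comparison of burden does not use this model, and at no dust effect the planned odds ratio was 0.99-1.00.

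**The Poisson model already handles repeated episodes.** It has a random effect for them, but it is a separate model and changes neither the case-crossover estimate nor its interval. Matching within patient removes differences between patients, not clustering over time within a patient.

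**The interval may be conservative.** This stands. A reader might infer that the planned intervals are too narrow in general. The documents give no recurrence pattern, and without bursts the interval was adequate or too wide.

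**Not all cases are AF.** This also stands. The section covers cardiac arrhythmia, and ventricular arrhythmia is a secondary outcome. Ongoing AF does not stop a ventricular episode from starting, so the at-risk argument is limited to AF episodes.

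**Conclusion.** The concern holds in a conditional form. For AF episodes, the control rule as written attenuates the onset odds ratio if dust raises AF onset: about 1.27-1.39 for a true 1.5 and 1.15-1.20 for a true 1.25, a loss of roughly 19-41% on the log scale. This rests on the planning burden and on assumed episode lengths and recurrence, so the direction is firmer than the size.

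It is tempting to read the size straight from the 15% burden: about 15% of control hours in AF, and 1.40 for a true 1.5. The documents do not support that. The 15% is an average over patients with an SD just as large, while controls are sampled per episode and high-burden patients supply most episodes.

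The interval is a separate and weaker point. It can be too narrow, modestly (ratio up to 1.30) in the hour-level runs and more so with many short clustered episodes, but only if episodes come in bursts.

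The change is worth making because this is one of two models that address the dust association in the primary objective. It does not bear on the randomised result.

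**What to change.** In the Case-Crossover section of the SAP, and the matching Protocol text, specify for AF episodes:

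1. The case is the onset of an episode.
2. Control hours in which the device log shows AF in progress are dropped.
3. Episodes separated by less than a pre-specified AF-free gap are merged into one case.
4. Standard errors are robust and clustered by patient.

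Items 2 and 4 belong together. With AF hours dropped, the model-based standard error becomes too small when episodes recur early: with 6 h episodes, K = 20 and a true ratio of 1.5 it was 0.026 against an empirical SD of 0.040, while the clustered value was 0.038. Dropping AF hours reduces the bias but does not always remove it: mean odds ratios ran from 1.42 to 1.56 for a true 1.5, and the low value with 2 h episodes reflects the one-hour grid. Item 3 was not simulated.

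Cost: SAP wording only, since the device recordings already capture the episodes. There will be fewer control hours (26-45% fell in AF in the hour-level simulations) and possibly wider intervals. With 12 h episodes, no bursts and a true 1.5, the empirical SD of the log odds ratio rose from 0.024 to 0.031.
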